Recent studies from our group and others in hospitalized patients with T2D have reported increased detection of both hypo- and hyperglycemic events with the use of CGM compared to POC BG testing 21,23-25. We also reported that the hospital use of the Glucose Telemetry System with Bluetooth technology allows CGM glucose values to be transmitted from the patient's bedside to a central monitoring device in the nursing station, reducing the frequency of hypoglycemia in insulin treated patients with T2D 26,27. More recently, in collaboration with the University of Maryland, reported significant reduction in the rate of hospital hypoglycemia in insulin treated medicine and surgery patients with T2D using the glucose telemetry system with real-time CGM 28. In addition, the use of Dexcom G6 CGM in insulin-treated patients revealed great accuracy, with 98.6% of reading within Clarke error Grid A and B (unpublished data, see preliminary results section). Thus, our experience in the hospital supports the use of the use of CGM for the management of patients with diabetes and prevention of hypoglycemia. However, we do not know if this experience can be extrapolated to individuals in long-term skilled nursing facilities. Therefore, in-depth analyses of glycemic control and potential benefit of RT-CGM in real-world is needed to determine whether the CGM-GTS can improve glycemic control and prevent hypoglycemia in vulnerable population of adult patients admitted to LTC facilities.

The primary aim is difference between POC testing and CGM-GTS in the frequency of hypoglycemia (safety outcome) and glycemic control (efficacy outcome) during admission.

- 1) Hypoglycemia <70 mg/dl and clinically significant hypoglycemia <54 mg/dl (safety outcome)
- 2) Glycemic control, as measured by time in range (TIR) between 80-180 mg/dl (efficacy outcome)

[figure not shown]
**Secondary outcomes** include differences between groups in any of the following measures:

1. Nocturnal hypoglycemia < 70 mg/dl and < 54 mg/dl (between 22:00 and 06:00)
2. Number of hypoglycemia events (< 70 and 54 mg/dl)
3. Time in hypoglycemia (<70 mg/dl) and hyperglycemia (>240 mg/dl)
4. Number of prolonged hypoglycemia > 1 and 2 hours by CGM
5. Frequency and time of hypoglycemic during the day and night
6. Frequency and duration or time on hyperglycemia > 240 mg/dl
7. Percentage of BG readings within target BG of 70 and 180 mg/dl
8. Glycemic variability calculated by standard deviation and MAGE

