## 6. Procedures Involved

Residents with T2D in subacute and long-term skilled nursing care facilities treated with insulin and/or insulin-secretagogues will be randomized to a standard of care group with POC testing or to real time Dexcom CGM with GTS for up to 60 days of admission.

Patients in the standard of care group will wear a blinded CGM and receive POC testing before meals and bedtime, with providers adjusting oral agents or insulin dose based on POC results. Patients in the intervention CGM group will have a single daily fasting POC testing and will wear a real-time Dexcom G6 with GTS, and providers will adjust oral or insulin therapy based on CGM-GTS profile information.

Nursing staff and primary care will receive education on the CGM technology by our research team.

Education efforts will include general information on the technology, how and when to remove or replace CGM sensors and transmitters, and the hypoglycemia prevention protocol. Treatment of hypoglycemia (POC <70 mg/dl) will be similar in both groups following a standard hospital protocol.

[figure not shown]
CGM alarm settings, and prevention of hypoglycemia protocol. Hypoglycemia alarm will be set to < 85 mg/dl (for prevention for low blood glucose levels). Nursing staff will be instructed to provide 15 grams of carbohydrates in response to a hypoglycemia alarm. For control group (blinded CGM) CGM alarms are turned off, however if the POC is found to be between <80 mg/dl by POC, 15 grams of carbohydrates will be given as a preventive measurement for hypoglycemia (standard of care).

The hyperglycemia alarm will be set at 300 mg/dl. If this occurs, the nursing staff will assess clinical status and perform a POC glucose testing to confirm glucose values. If BG > 300 mg/dl, nursing staff will communicate the high glucose value to the primary care team.

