The present aims of this RCT is to investigate whether the Dexcom G6 CGM with Glucose Telemetry System (CGM-GTS) with hypoglycemia alarm may reduce the risk of hypoglycemia < 70 mg/dl (safety outcome) and improve glycemic control as measured by the percent of time in range (TIR) 70-180 mg/dl (efficacy end-point) in patients with T2D in subacute and long-term skilled nursing care facilities. Patients in the standard of care group will wear a blinded CGM and receive POC testing before meals and bedtime, with providers adjusting oral agents or insulin dose based on POC results. Patients in the intervention CGM group will have a single daily fasting POC testing and will wear a real-time Dexcom G6 with GTS, and providers will adjust oral or insulin therapy based on CGM-GTS profile information. [name], PhD at the School of Public Health at Emory University will conduct statistical analyses.

For the safety endpoint, we will first compare the proportions of patients who have at least one episode of hypoglycemia by POC and by CGM. We will first perform nonparametric comparisons of the rate of hypoglycemia based on a two-sided Chi-square test (or Fisher's exact test in the presence of low incidence rates), followed by the Cochran-Mantel-Haenszel test, which adjusts for the potential center effect. Then we will perform univariate Poisson regression (or Negative Binomial regression) to assess whether there is any difference in the number of clinically significant hypoglycemia events between the two treatment groups. We will further conduct multivariate Logistic regression, Poisson regression (or Negative Binomial regression) to estimate the difference in the rate and frequency of hypoglycemia while adjusting for potential confounders. A glucose value < 70 mg/dl is considered as hypoglycemia requiring a nurse-driven response; thus, a BG <70 mg/dl will be used for sample size calculation. Data from Singh et al a reduction of hypoglycemia was reported comparing the CGM/GTS system than POC (Singh et al 2020) per patient (0.67 episodes per patient, 95% CI 0.34-1.30

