versus 1.69 episodes per patient, 95% CI 1.11-2.58,  $p= 0.024$ ) . Based on the results of the recent glargine U100 vs U300 study using CGM monitoring in the hospital, 56% had CGM BG readings <70 mg/dl (vs 14% with POC testing-standard of care), it is reasonable to assume 60% of resident on LTC facilities will experience one or more BG < 70 mg/dl by CGM. If we assume that 35% in the standard of care group will have at least one BG <70 mg/dl (based on linagliptin LTC study) , using one-sided, two-sample t-tests, we require we will need 70 patients per group to achieve 80% power.

Hypoglycemia incidence, Rate in the CGM intervention group	30%	35%	40%	45%	50%
Estimated sample size (N/group) for 80% power	49	70	107	186	407

For the efficacy endpoint, we will compare mean daily glucose levels measured by CGM or POC, and percent TIR measured by CGM between treatment groups by nonparametric Wilcoxon-tests or two-sample t-tests, and by multivariate linear regression, which adjusts for other potential confounders such as age, gender, BMI, center, and admission HbA1c. A logarithm transformation may be employed to make the data better conform to the normality assumption. When conducting multivariate regression analyses, we will apply standard variable selection and model checking procedures to decide the final model. Stepwise, backward, or forward model selection strategy will be adopted to determine the variables to be included in the final model. Standard diagnostic and model checking procedures, such as deviance residual plot and Hosmer- Lemeshow test, will be applied to examine the fit of the developed models. To show non-inferiority between POC and CGM in terms of glycemic control, we set the equivalence margin of 18 mg/dl (1 mosm/l), from a view that a difference <18 mg/dl is usually not considered as clinically significant . Based on the results from our recent CGM trials , it is reasonable to assume the standard deviation of mean daily BG is bounded above by 45 mg/dl. Assuming the true BG difference between the treatment groups is zero, and using one-sided, two-sample t-tests, we require 70 subjects for each treatment group to achieve 80% power.

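### The efficacy aim is to improve time in range, but the only efficacy hypothesis that is sized is non-inferiority of mean daily glucose, an unlisted measure whose test has no stated role, direction or alpha

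*Combined protocol and SAP*

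**What the plan says.** **Aim.** The statistical part of Section 18 (Data management and statistical analysis) gives the efficacy aim a direction: "improve glycemic control as measured by the percent of time in range (TIR) 70-180 mg/dl (efficacy end-point". Section 4 makes TIR the primary efficacy outcome but words the aim neutrally: "The primary aim is difference between POC testing and CGM-GTS in the frequency of hypoglycemia (safety outcome) and glycemic control (efficacy outcome". The lower bound of the range also differs there: "Glycemic control, as measured by time in range (TIR) between 80-180 mg/dl (efficacy outcome". Section 1 uses 80-180 as well.

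**Planned comparison.** For the efficacy endpoint Section 18 says "we will compare mean daily glucose levels measured by CGM or POC, and percent TIR measured by CGM between treatment groups", by Wilcoxon or t-test and by multivariable linear regression.

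**Sized hypothesis.** The same paragraph then says: "To show non-inferiority between POC and CGM in terms of glycemic control, we set the equivalence margin of 18 mg/dl". The inputs are a zero true difference, one-sided two-sample t-tests, 80% power and 70 per group, with this on variability: "it is reasonable to assume the standard deviation of mean daily BG is bounded above by 45 mg/dl". No alpha is given.

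**Size.** Sections 1 and 12 plan 100 participants in total. The allocation ratio is not stated.

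**The concern.** The aim and the sized hypothesis differ in both variable and type. The aim is improvement in TIR. The sized test asks whether mean daily glucose is not unacceptably different, and it assumes no difference at all. Mean daily glucose appears in neither the primary nor the secondary list in Section 4, and no objective mentions non-inferiority. The text calls the 18 mg/dl figure an equivalence margin inside a sentence about non-inferiority, so it is unclear whether one direction or two is tested.

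What is at stake is the wording of the efficacy conclusion. If TIR shows no gain and mean glucose falls within the margin, the plan does not say which result decides the efficacy outcome. A reader of the trial report could take the 80% power in Section 18 as applying to TIR, which it does not.

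**Working it through.** **1. The two efficacy analyses side by side**

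| | Percent TIR | Mean daily glucose |
|---|---|---|
| Listed outcome in Section 4 | yes, primary | no |
| Stated hypothesis | none beyond the aim | non-inferiority / equivalence |
| Margin or target difference | none | 18 mg/dl |
| SD | none | 45 mg/dl (upper bound) |
| Alpha | none | one-sided, level not given |
| N and power | none | 70 per group, 80% |
| Glucose source | CGM | CGM or POC |

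**2. The plan's own figure.** Inputs from Section 18: margin 18, SD 45, true difference 0, power 80%. Alpha is an assumption, so two levels are shown.

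n per group = 2 × [SD × (z for 1−alpha + z for power) / margin]²

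- One-sided 0.05: 2 × [45 × (1.645 + 0.842) / 18]² = 77.3, so 78.
- One-sided 0.025: 2 × [45 × (1.960 + 0.842) / 18]² = 98.1, so 99.
- Two-directional equivalence (two one-sided tests at 0.05): 2 × [45 × (1.645 + 1.282) / 18]² = 107.1, so 108.

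None of these gives 70. With 70 per group, non-inferiority power is about 76% (one-sided 0.05) or 66% (0.025). With 50 per group (100 in total at an assumed 1:1) it is about 64% or 52%. If equivalence is meant, power at 0.05 is about 53% (70 per group) or 28% (50 per group).

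**3. What a passing result can look like.** Non-inferiority is declared when the observed difference (CGM arm minus POC arm) plus t × SE is below 18, where SE = 45 × √(2/n). The largest observed worsening that still passes is therefore 18 − t × SE.

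| Per arm | SE | One-sided 0.05 | One-sided 0.025 |
|---|---|---|---|
| 50 | 9.00 | 18 − 1.661 × 9.00 = 3.1 mg/dl | 18 − 1.984 × 9.00 = 0.1 mg/dl |
| 70 | 7.61 | 18 − 1.656 × 7.61 = 5.4 mg/dl | 18 − 1.977 × 7.61 = 3.0 mg/dl |

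If the CGM arm is truly 5 mg/dl worse, the chance of declaring non-inferiority (normal approximation) is 42% at 50 per arm and 53% at 70 per arm with one-sided 0.05. With 0.025 it is 30% and 40%.

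**4. What the TIR comparison can detect.** Two-sided 0.05, 80% power: detectable difference = (1.960 + 0.842) × √(2/n) in SD units, which is 0.56 SD at 50 per arm and 0.47 SD at 70 per arm. The documents give no SD for TIR. If it were 15, 20 or 25 percentage points (assumption), 50 per arm would detect 8.4, 11.2 or 14.0 points, and 70 per arm 7.1, 9.5 or 11.8 points.

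**The case against.** The strongest reply is that TIR is tested. Section 18 compares percent TIR between arms before it mentions a margin, and a superiority test needs no margin. This stands. A reader might infer that the plan cannot answer its efficacy objective, and the documents do not support that. What is missing is the statement and sizing of the TIR hypothesis, not the analysis.

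Second, nothing in the protocol says that non-inferiority alone counts as meeting the efficacy outcome. It may have been meant as a check that fewer lows were not bought with higher glucose. This also stands. The fault is that the role is not stated.

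Third, a reader might expect the alarm response in Section 6 to push mean glucose up in the CGM arm: "Nursing staff will be instructed to provide 15 grams of carbohydrates in response to a hypoglycemia alarm". The documents do not settle the direction. The same section also gives control residents carbohydrate at a POC reading below 80 mg/dl, CGM-arm therapy is adjusted on the CGM profile, and there is a 300 mg/dl alarm.

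Fourth, a reader might convert the whole 18 mg/dl into lost TIR. With assumed normal readings (mean 160, SD 45), a true 18 mg/dl shift would take TIR 80-180 from about 63% to 50%. But that is the shift the test is built to exclude, and at that true difference it passes only with probability alpha. In the same model, the largest passing observed differences at one-sided 0.05 (3.1 and 5.4 mg/dl) correspond to about 2.0 and 3.6 TIR points.

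**Conclusion.** The concern holds as a mismatch between aim and stated hypothesis. The efficacy aim is improvement in TIR, and the TIR comparison is planned but has no stated hypothesis, alpha, target difference or power. The one sized efficacy hypothesis is on a measure outside the outcome list, with no defined role, direction or alpha. Passing it would show only that mean glucose is not worse by 18 mg/dl or more.

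The observed worsening that could still pass is modest: 3.1 mg/dl (50 per arm) or 5.4 mg/dl (70 per arm) at one-sided 0.05, and about 0.1 or 3.0 mg/dl at 0.025. These limits rest on SD 45, 1:1 allocation and an alpha the plan does not give. At 50 per arm and 0.025 there is almost no room for observed worsening, but a pass would still not be evidence of improvement.

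The plan should be changed, because the change governs what the trial may conclude. It is not evidence that the trial would report worse control as success.

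**What to change.** In Sections 4 and 18:

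1. State the efficacy hypothesis as superiority of CGM-GTS on CGM-measured percent TIR, tested two-sided at a stated alpha.
2. Use one TIR range throughout, after reconciling 80-180 (Sections 1 and 4) with 70-180 (Section 18).
3. List mean daily glucose as a secondary outcome, measured by CGM in both arms. Control residents already wear a blinded sensor. POC is taken before meals and at bedtime in one arm but once daily, fasting, in the other, so POC means are not comparable.
4. Label the 18 mg/dl test as a supportive, one-directional non-inferiority check with a stated alpha. Drop the word equivalence, and say that a pass supports only that mean glucose is not worse by 18 mg/dl or more.
5. State that the 80% power in Section 18 does not apply to TIR, and report the detectable TIR difference at the planned size: about 0.56 SD at 50 per arm, two-sided 0.05, 80% power.

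The change is to wording; the data and tests are already planned. The cost is a less favourable efficacy claim, since non-inferiority could not be presented as improved control, and a TIR test whose power depends on an SD the documents do not give.

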## 1. Study Summary

Study Title	Randomized Controlled Trial To assess the Benefits of Dexcom Continuous Glucose Monitoring with Glucose telemetry System for the Management of Diabetes in Long-term Care Setting: The CGM-GTS in Long-term care
Study Design	Randomized Controlled Trial
Primary Objective	To compare differences in frequency of hypoglycemia (<70 mg/dl) and glycemic control (time in range [TIR] 80-180 mg/dl) between the Dexcom CGM with Glucose Telemetry System (CGM-GTS) compared to a standard of care protocol, in residents with T2D treated with insulin and/or insulin-secretagogues, in subacute and long-term skilled nursing care facilities.
Secondary Objective(s)	Determine differences in clinical outcomes (number of complications, ER visits and need for hospital re-admissions), and health care utilization between the use of real-time Dexcom CGM Glucose Telemetry System (CGM-GTS) compared to a standard of care in patients with T2D in subacute and long-term skilled nursing care facilities.
Research Intervention(s)/Interactions	POC testing or to real time Dexcom CGM with GTS for up to 60 days of admission.
Study Population	Adult residents with T2D in subacute and long-term skilled nursing care facilities treated residents with T2D treated with insulin and/or insulin-secretagogues.
Sample Size	100
Study Duration for individual participants	Length of admission to subacute and long-term skilled nursing care facilities or up to 60 days (whichever comes sooner)
Study Specific Abbreviations/ Definitions	T2DM: Type 2 Diabetes Mellitus OADs: oral antidiabetic medications CGM: continuous glucose monitor GTS: glucose telemetry system LTC: Long Term Care SSI: Sliding Scale Insulin
Funding Source (if any)	Dexcom, Inc.

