### **12. Local Number of Participants**

*The total number of participants to be accrued locally is 100.*

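### The 18 mg/dl non-inferiority margin is tied only to an unadjusted t-test; the planned regression with admission HbA1c and center has no fixed covariates and no stated link to the margin

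*Combined protocol and SAP*

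**What the plan says.** All of the analysis text is in Section 18, under the data management and statistical analysis sub-heading.

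- **Comparison.** Mean daily glucose and percent time in range (TIR) are compared "between treatment groups by nonparametric Wilcoxon-tests or two-sample t-tests", and also by a linear regression that "adjusts for other potential confounders such as age, gender, BMI, center, and admission HbA1c". The variables kept in the final regression are chosen by a stepwise, forward or backward procedure.
- **Non-inferiority.** For glycemic control, "we set the equivalence margin of 18 mg/dl". The inputs are that "the standard deviation of mean daily BG is bounded above by 45 mg/dl" and "Assuming the true BG difference between the treatment groups is zero". The sentence ends: "using one-sided, two-sample t-tests, we require 70 subjects for each treatment group to achieve 80% power".
- **Alpha.** None is given for this test.
- **Size.** The Study Summary gives "Sample Size 100", and Section 12 says "The total number of participants to be accrued locally is 100".
- **Efficacy outcome.** Sections 1, 4 and 18 name TIR. Mean daily glucose is in neither the primary nor the secondary list of Section 4; its role in the efficacy analysis is set out only in the statistical text.

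**The concern.** A non-inferiority conclusion depends on one number: whether the confidence limit for the arm difference stays inside the margin. The analysis that produces that limit should be named in advance. Here the only method attached to the margin is an unadjusted t-test, and it is attached through the sample-size sentence rather than an analysis statement.

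The regression could give a tighter interval. Admission HbA1c reflects earlier glucose levels, so it can be expected to predict mean daily glucose during the stay, and the plan already expects to have it. As written, though, the regression cannot serve as the pre-specified non-inferiority analysis, for two reasons. Automated selection may discard HbA1c or center. A nominal interval computed after selection also takes no account of the selection, so it is not a valid pre-specified interval.

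The precision of this comparison is at stake in a trial whose planned total of 100 is below the 140 (2 × 70) that its own calculation asks for. There is also the freedom to choose among a t-test, a Wilcoxon test and several regressions once the data are seen.

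**Working it through.** **Inputs from Section 18:** margin 18 mg/dl, SD 45 mg/dl (an upper bound), true difference 0, one-sided two-sample t-test. **From Sections 1 and 12:** N = 100, taken as 50 per arm (1:1 allocation is an assumption). **Assumed, because the documents are silent:** one-sided alpha 0.05, with 0.025 as the alternative, and a correlation ρ of 0.3 to 0.6 between admission HbA1c and mean daily glucose.

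**Step 1: the plan's own figure.** n per group = 2 × (z₁₋α + z₀.₈)² × (SD/margin)², with (45/18)² = 6.25.

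- Alpha 0.05: 2 × (1.645 + 0.842)² × 6.25 = 77.3, so 78 per group.
- Alpha 0.025: 2 × (1.960 + 0.842)² × 6.25 = 98.1, so 99 per group.

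The stated 70 is not reproduced at either level. With 70 per group, power is 76.1% at 0.05 and 65.2% at 0.025 (noncentral t). An SD of about 42.8 would be needed for 70 to give 80% at alpha 0.05.

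**Step 2: unadjusted power at 50 per arm.** SE = 45 × √(2/50) = 9.0 and the noncentrality is 18/9.0 = 2.0 on 98 df. Power is 63.4% at 0.05 and 50.8% at 0.025.

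**Step 3: adjusted power at 50 per arm.** Residual SD = 45 × √(1 − ρ²), and the noncentrality is 18/(residual SD × √(2/50)).

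| ρ | Residual SD | Power, alpha 0.05 | Gain (points) | Power, alpha 0.025 | Gain (points) |
|---|---|---|---|---|---|
| 0 | 45.0 | 63.4% | – | 50.8% | – |
| 0.3 | 42.9 | 66.9% | 3.5 | 54.6% | 3.8 |
| 0.4 | 41.2 | 69.9% | 6.6 | 58.0% | 7.1 |
| 0.5 | 39.0 | 74.2% | 10.8 | 62.8% | 12.0 |
| 0.6 | 36.0 | 79.9% | 16.5 | 69.7% | 18.9 |

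Two terms for three facilities, one for HbA1c and one for a missing-value indicator take the df from 98 to 94. That changes power by at most 0.1 point. No gain from center is included.

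**Step 4: what this means for the confidence limit.** Unadjusted, the one-sided limit lies 1.661 × 9.0 = 14.9 mg/dl beyond the observed difference at alpha 0.05, and 1.984 × 9.0 = 17.9 at 0.025. The trial then passes only if the observed unfavourable difference is below about 3 mg/dl, or about 0.1 mg/dl. At ρ = 0.5 the SE is 7.79 and the distances are 12.9 and 15.5, so the room grows to about 5.1 and 2.5 mg/dl.

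**Step 5: does adjustment repair the sample size?** Using the Step 1 formula with residual SD 39.0, 80% power needs 58 per arm at alpha 0.05 and 74 at 0.025. At ρ = 0.5, therefore, 50 per arm is still too few.

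**The case against.** A reader might infer that the plan makes the unadjusted t-test decisive, ignores HbA1c and center, and so loses 11 points of power. The documents do not support that. No sentence calls the t-test decisive. The same text plans a regression naming both variables. Sizing on an unadjusted test while also planning an adjusted analysis is ordinary conservative practice. If the regression decides and keeps HbA1c, the loss disappears.

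The size is also uncertain. The correlation appears nowhere in the documents. Treatment may be changed after randomization and follow-up runs to 60 days, either of which could weaken it. Section 19 lists only laboratory results at baseline, so the timing and completeness of HbA1c are unknown. The SD of 45 is an upper bound: a raw SD of 36, for example, would give about 80% power without any adjustment (last row of the table). Finally, mean daily glucose is not a listed endpoint, and no gain is worked out for TIR.

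All of this stands, and it limits the claim. It does not remove the gap. The margin is attached only to the t-test, no text applies it to the regression, and automated selection means that nobody can say in advance whether HbA1c and center will be in the model.

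**Conclusion.** The plan does not name the analysis that decides non-inferiority on mean daily glucose. Its only adjusted analysis leaves the covariates to data-driven selection.

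The power cost is conditional. If the unadjusted test decides, with 50 per arm, SD 45 and no true difference, power is about 63% at an assumed one-sided 0.05. Adjustment would bring 67% to 80% over correlations of 0.3 to 0.6. At 0.025 it is 51% against 55% to 70%. The gain is therefore roughly 4 to 17 points at 0.05, and the 11-point figure belongs to a correlation of 0.5 alone.

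It would also be wrong to infer that the whole efficacy conclusion rests on this margin, because the stated efficacy outcome is TIR. Nor does adjustment settle the two larger sample-size faults seen here: 70 per group does not follow from the stated inputs, and a total of 100 is below 70 per group. Those need their own correction.

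**What to change.** State in Section 18 that non-inferiority is judged on the treatment coefficient, and its one-sided confidence limit in mg/dl against the 18 mg/dl margin, from a linear model of mean daily glucose on arm, center and admission HbA1c. State the alpha. Fix these covariates in advance and exempt them from variable selection. Handle a missing HbA1c with a missing-value indicator so that no resident is dropped.

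Use the same fixed-covariate model for percent TIR. Keep the unadjusted t-test or Wilcoxon test as supporting analyses, and label any model reached by variable selection as exploratory.

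The change is a few sentences, with no new procedures and no data beyond what the plan already expects to have. The statistical cost is 3 to 4 degrees of freedom out of 98, which is negligible at 50 per arm. If HbA1c turns out to be weakly related to glucose, the gain is small but almost nothing is lost.
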